Secondary Outcome	 Combined incidence of all-cause mortality or non-fatal stroke at 72 hours post-TAVI, or hospital discharge (if sooner) Combined incidence of all-cause mortality, non-fatal stroke or transient ischaemic attack at 72 hours post-TAVI or hospital discharge (if sooner) Incidence of all-cause mortality at 72 hours post-TAVI or hospital discharge (if sooner) Win ratio for all-cause mortality, disabling stroke and non-disabling stroke at 72 hours post-TAVI, or hospital discharge (if sooner) Incidence of all-cause mortality at 12 months post-TAVI Incidence of all-cause mortality up to the end of the trial. This will use trial data up to 12 months, and centrally held NHS data from 12 months to the end of the trial Incidence of stroke as defined by centrally held NHS data (described in section 14.7) between 72 hours post-TAVI or hospital discharge (if sooner) and 30-days post-TAVI Incidence of stroke as defined by centrally held NHS data (described in section 14.7) between 30-days post-TAVI and the end of the trial Stroke severity assessment in participants who have had a stroke within 72-hours post-TAVI or hospital discharge (if sooner) Disability Outcome assessed up to 12 months post-TAVI in participants who have had a stroke within 72-hours post-TAVI or hospital discharge (if sooner) Cognitive Outcome assessed up to 12 months post-TAVI (collection of cognitive outcome data now discontinued; see section 7.2) Vascular access site related complications at 72-hours post-TAVI or hospital discharge (if sooner) and between 6-8 weeks post-TAVI Cost-effectiveness analysis at 12 months post-TAVI
Sample Size	9712
Planned Trial Period	Planned start date: 01 August 2020 Planned end date: 31 August 2027 Total project duration: 85 months Individual participant involvement: 12 months after TAVI procedure
Planned Recruitment period	58 months

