7.2. Key Secondary outcomes

- **1.Combined incidence of all-cause mortality or non-fatal stroke** at 72 hours post-TAVI or hospital discharge (if sooner). Stroke will be assessed as defined in section 7.1.2.
- **2.** Combined incidence of all-cause mortality, non-fatal stroke or transient ischaemic attack at 72 hours post-TAVI or hospital discharge (if sooner).
- 3. Incidence of all-cause mortality: at 72 hours post-TAVI or hospital discharge (if sooner)
- **4**. **Win ratio for all-cause mortality, disabling stroke and non-disabling stroke** at 72 hours post-TAVI, or hospital discharge (if sooner)
- 5.Incidence of all-cause mortality: at 12 months post-TAVI.
- **6. Incidence of all-cause mortality:** up to the end of the trial. This will use trial data up to 12 months, and centrally held NHS data from 12 months to the end of the trial
- **7.** Incidence of stroke as defined by centrally held NHS data (described in section 14.7): Identified between 72 hours post-TAVI or hospital discharge (if sooner) and 30-days post-TAVI.
- **8.** Incidence of stroke as defined by centrally held NHS data (described in section 14.7): Identified between 30-days post-TAVI and the end of the trial.
- **9. Stroke Severity:** In participants who had a stroke within 72-hours post-TAVI or hospital discharge (if sooner) will be assessed using the National Institutes of Health Stroke Scale (NIHSS). This measure has been adopted as a secondary outcome to explore the association between use of the CEP and prevention of large cerebral vessel occlusion (LVO). Strokes with an NIHSS score of 10 or greater will be defined as severe.
- **10. Disability Outcome:** Stroke recovery and/or ongoing disability in participants who had a stroke within 72-hours post-TAVI or hospital discharge (if sooner) will be assessed with the smRSq at discharge and between 6-8 weeks post-TAVI and at 12-months post-TAVI.

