10.8.3. Visit 2 – 12 months post-TAVI

This will be conducted by telephone for the study, however if there is a pre-scheduled clinical visit, it can be done in person.

Contact with the patient will be arranged by a delegated member of the research team at the local hospital. Phone calls are projected to take no more than 10 minutes to complete the EQ-5D-5L questionnaire. The staff contacting the patient will check electronic records prior to contacting the patient to ensure they have not died. While participant preferences for contact will take priority, we advise that after 3 unsuccessful attempts to reach the patient, no further attempts are made.

Secondary outcomes assessed:

- Mortality status
 - Taken from patient notes
- smRSq
 - Short questionnaire administered for the study
- EQ-5D-5L
 - Short questionnaire administered for the study

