14.6. Health Economics Analysis

A cost-effectiveness model will be developed to estimate the short-term (1-year) and longer-term (lifetime) survival and quality-adjusted life years (QALYs) and the costs incurred by the NHS and Personal Social Services (PSS). The analysis will also address whether value for money could be further optimised within the overall TAVI population (e.g. using additional risk stratification). In addition to the primary and secondary trial endpoints, we will prospectively link the trial participants to collect further data until the end of their participation in the trial on subsequent stroke and other events (from Hospital Episode Statistics [HES], hospital resource utilisation [HES] and mortality (Office for National Statistics [ONS]). The linkages to HES and ONS will provide a more complete picture of the short and longer-term costs and outcomes and will enhance the precision and robustness of the cost-effectiveness results. Resource utilisation during the initial index admission will be collected. This will include information on the duration of the procedure, any additional procedures and consumables and the duration of the initial index admission (including any periods in ICU). To estimate healthcare costs, we will assign national average costs using NHS Reference costs and PSSRU (Personal Social Services Research Unit) unit cost estimates. We will collect quality of life measures using the standardised EQ-5D-5L at baseline and at 12 months to estimate QALY changes over the 12-month follow-up. The longer-term model will extend the time horizon to a lifetime. The model will take into account uncertainty in the evidence base (including risk of events, outcomes and costs). Our results will determine the probability of CEP being cost-effective, conditional on various levels of willingness-to-pay values for gain in health benefit. Sensitivity analyses will be conducted to evaluate the impact of alternative model assumptions.

14.7. Use of centrally held data to assess long-term stroke and mortality follow-up in patients recruited at NHS sites.

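### Item 6 of section 7.2 takes deaths before month 12 from trial data although linked death records will cover those months, so a death unknown to the site can be missed in both items 5 and 6.

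*Protocol*

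**What the plan says.** - **Mortality to the end of the trial (Protocol 7.2, item 6; repeated in the Synopsis and the section 7 table).** The source is fixed by period: "This will use trial data up to 12 months, and centrally held NHS data from 12 months to the end of the trial".
- **Mortality at 12 months (Protocol 7.2, item 5).** The outcome reads "5.Incidence of all-cause mortality: at 12 months post-TAVI", and no data source is attached to it.
- **How sites learn vital status (Protocol 10.8.3).** At the 12-month visit, mortality status is "Taken from patient notes". Before any call, staff must "check electronic records prior to contacting the patient to ensure they have not died".
- **Linkage for clinical outcomes (Protocol 14.7).** Participants recruited at NHS sites are linked to HES and to mortality data. No start at month 12 and no 12-month stop is given. Item 7 of section 7.2 already uses centrally held data for stroke between 72 hours (or discharge) and 30 days.
- **Linkage for health economics (Protocol 14.6).** Here "we will prospectively link the trial participants to collect further data until the end of their participation in the trial", with the sources including "mortality (Office for National Statistics [ONS"]). The Synopsis gives the length of participation: "Individual participant involvement: 12 months after TAVI procedure".

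**The concern.** Item 6 makes the data source part of the outcome definition, and for the first 12 months it names the source that is more likely to be incomplete. TAVI is done in specialist centres (section 8), and patients may be approached through participant identification centres (section 10.1). A death at home or in another hospital need not reach the notes that the research team reads.

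If a site does not know of a death in month 8, that participant is not a death in item 5. Under item 6 the central records are read from month 12, so an event in month 8 falls outside the window assigned to them. The death is lost from both outcomes although its date may sit in an extract that the trial holds.

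At stake are the absolute mortality risks and the risk difference, which section 14.1 extends to the secondary outcomes. The trial's two accounts of the first year may also disagree, since the 1-year economic model draws on ONS deaths.

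**Working it through.** **Step 1. Is there a stated figure to reproduce?** Not for this point. The protocol gives no 12-month mortality rate, no effect size or power for mortality, and no expected share of deaths missed by sites. Its one sample-size calculation is for 72-hour stroke. It reproduces (3% versus 2%, two-sided 5%, 80% power: 3826 per arm, 7652 in total; 7652 / 0.99 = 7730 after rounding up) and is not touched here.

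**Step 2. Sources side by side.**

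| Use | Months 0 to 12 | After month 12 |
|---|---|---|
| Item 5, 12-month mortality | Site notes, by inference from 10.8.3 | not applicable |
| Item 6, mortality to trial end | Trial data (stated) | Central NHS data (stated) |
| Item 7, stroke from 72 hours to 30 days | Central NHS data (stated) | not applicable |
| 14.6, 1-year economic model | ONS mortality linked (stated) | not applicable |
| 14.7, linked mortality, NHS sites | No start date that excludes these months | Yes |

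Linked deaths for months 0 to 12 are therefore to be obtained, but no passage says that they count towards, or are reconciled with, items 5 and 6. Section 14.6 itself gives completeness, in the short term as well as the longer term, as a reason for linking.

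**Step 3. Illustration of size.** Inputs: N = 9712 (section 14.2.1), hence 4856 per arm at 1:1. Assumed: 12-month mortality *p* and share of deaths missed by sites *m*. Deaths lost = N × p × m.

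| Assumed p | m = 1% | m = 5% | m = 10% |
|---|---|---|---|
| 5% | 5 | 24 | 49 |
| 10% | 10 | 49 | 97 |
| 15% | 15 | 73 | 146 |

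For example, 9712 × 0.10 × 0.05 = 48.6.

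**Step 4. Effect on the comparison.**

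- *Equal shares missed.* Observed risks are p₁(1 − m) and p₀(1 − m). The risk ratio is unchanged and the risk difference shrinks by the factor (1 − m). With an assumed true risk ratio of 0.85, p = 10% in controls and m = 10%, power falls from 72% to 67%.
- *Unequal shares missed, true risk ratio 1.* The apparent risk ratio is (1 − m₁)/(1 − m₀). For 5% versus 3% missed it is 0.95/0.97 = 0.979. With p = 10%, the observed risks are 9.5% and 9.7%, the standard error is √[(0.095 × 0.905 + 0.097 × 0.903)/4856] = 0.0060, and the shift is d = 0.002/0.0060 = 0.33. The two-sided error Φ(d − 1.96) + Φ(−d − 1.96) is then 6.3%. It is 5.6% at p = 5% and 7.1% at p = 15%.

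The unequal case is a sensitivity calculation. The trial is open label at sites (section 10.5), but nothing in the protocol indicates that death capture would differ by arm.

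**The case against.** The case on the other side has real weight.

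- **Nothing says that early linked deaths will be ignored.** Item 6 assigns a source to each period without the word only, and item 5 names no source. The statistical analysis plan, not shown here, may set out a reconciliation. This stands in part: for item 5 the reliance on site notes is an inference. For item 6 the division is written into the outcome definition, so a plan that counted linked deaths before month 12 would depart from the protocol's wording.
- **Sites have a safeguard.** The electronic-records check before each call will find many deaths. The protocol does not say which records are meant, so its completeness cannot be judged, but the number missed may well be small.
- **Site data cover more people.** Section 14.7 links NHS-site participants only, and section 21.2 shows that private hospitals may recruit. Replacing site data as the main source would open a different gap. This stands, and the fix adds linked deaths to site deaths.

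Three stronger readings are tempting but are not supported:

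1. A reader might infer that vital status is lost when calls fail, because "after 3 unsuccessful attempts to reach the patient, no further attempts are made". That limit is advisory and concerns contact with the patient for the EQ-5D-5L. Mortality status is collected separately, from notes, so a failed call does not make it unknown.
2. A reader might infer from section 14.6 that linkage ends 12 months after TAVI and so cannot serve items 6 and 8. That section describes the health economics data. Long-term stroke and mortality linkage is in section 14.7, which sets no 12-month stop.
3. A reader might infer that dead participants will be carried as alive for years. That assumes an analyst disregards a death date already in hand, or treats unknown status as alive. The protocol says neither.

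**Conclusion.** The point holds in a limited form. The stated rule for item 6, and by inference the source for item 5, leave out linked death records for the first 12 months although the trial is to obtain them. Applied literally, a death before month 12 that the site does not know of is missed in both outcomes, and the clinical and economic analyses may give different death counts for the same year.

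The size cannot be derived from the protocol. The counts above (5 to 146 deaths across the grid) rest wholly on assumed mortality and assumed missed shares, and the true number may be near or below the low end. If capture is equal between arms, the risk ratio is not biased, and what suffers is absolute risk, the risk difference and a little power. Only secondary outcomes are affected; the primary stroke outcome is not.

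**What to change.** Reword items 5 and 6 of section 7.2, and the matching lines in the Synopsis and the section 7 table, so that:

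- a death from randomisation onward counts if it is found in site data or in linked records, up to 12 months for item 5 and to the end of the trial for item 6;
- the two sources are reconciled, with a rule for conflicting dates;
- site data are used alone for participants who cannot be linked, namely those at private hospitals outside section 14.7 and those whose withdrawal bars further data (for the latter, up to the date of withdrawal, where they let earlier data be kept).

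The economic analysis should use the same reconciled deaths for the first year. A short table of deaths by source (site only, linked only, both) and by arm would show how much the change mattered and whether capture differed between arms.

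The cost is a wording amendment and a reconciliation step, since the linkage is already planned. The one drawback is that the final 12-month mortality result may have to wait for the linked extract.

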7.1.3. Adjudication of Primary outcome

The outcomes at 72-hours will be adjudicated by an independent Clinical Events Committee (CEC) using a standard protocol to limit bias (see section 17.3). The CEC will be blinded to trial treatment.

In addition to adjudicating the stroke outcomes, the CEC will be asked to identify a systematic approach to the identification of periprocedural hypotension so that its contributory role to any stroke outcome may be consistently applied. While most are expected to be embolic, there will be a small number of patients who have haemodynamic events for instance, following peri-procedure cardiac arrest. Any difference in stroke mechanism between the arms of the trial will be explored in the secondary analyses.

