14.2. Sample Size Determination

If the proportion experiencing the primary outcome is 3% in the control arm, we will require 7652 patients to detect a 33% relative risk reduction (risk ratio 0.67) to 2%. Assuming 1% losses/withdrawals we will recruit 7730, for 80% power and 5% significance. For the secondary combined outcome of all-cause mortality or stroke at 72 hours, a trial of 7730 would also provide very good power. For example, for a 33% relative reduction from a combined rate of 4.2% a trial of 7730 would provide power well in excess of 90%.

The event rate for the primary outcome is based on a review of published data from randomised trials and registries. Self-reported stroke rates in registries are less than those reported in randomised trials, where there is more active stroke ascertainment. A recently published patient level analysis reported a 72-hour stroke rate of 5.4% in the control group, and the recently published meta-analysis shows stroke rates of 6%. In the UK registry the self-reported incidence was 2.6% in 2017. We believe that by using a structured approach using the QVSFS the stroke ascertainment rate is likely to be higher. We have been conservative in our predicted event rate for all stroke at 3%, which is still nearly half of that reported in previous randomised TAVI trials.

Previous published studies suggest a potentially large impact of CEP on reducing incidence of stroke. However, these are not based on well-powered randomised trials and may overestimate efficacy. Therefore, the proposed effect size is based on more conservative estimates in comparison to data published from observational studies or small-randomised trials, while still representing a clinically meaningful reduction in stroke.

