14.2.1. Sample size increase

To maximise the chance of delivering a definite result for the trial, the sample size was increased from 7730 to 9712.

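### Stroke severity and disability are defined only among participants who had a stroke; comparing the arms there is not a randomised comparison and, at the design effect, multiplies the severe-stroke risk ratio by 1.5

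*Protocol*

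**What the plan says.** Section 7.2 lists severity as key secondary outcome 9: "In participants who had a stroke within 72-hours post-TAVI or hospital discharge (if sooner) will be assessed using" the NIHSS. It gives the reason for the outcome as "to explore the association between use of the CEP and prevention of large cerebral vessel occlusion (LVO") and sets NIHSS 10 or more as the threshold for a severe stroke. Outcome 10 is "Stroke recovery and/or ongoing disability in participants who had a stroke within 72-hours post-TAVI" (or by discharge if sooner), measured with the smRSq at discharge, 6-8 weeks and 12 months. The synopsis and the section 7 table confine both outcomes to the same group.

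The other text that bears on this point:

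- The section 7 table places these outcomes under a secondary objective that asks whether routine CEP improves stroke, mortality and disability outcomes.
- Section 14.1 says secondary clinical outcomes follow the primary approach (risk ratio and risk difference). It gives no denominator for outcomes 9 and 10.
- Section 14.3 defines the intention-to-treat population as participants whose TAVI procedure is started, analysed as randomised.
- Outcome 4, the 72-hour win ratio, ranks death, disabling stroke and non-disabling stroke and is not restricted to stroke patients.

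**The concern.** Whether CEP prevents severe or disabling stroke is a question about how many participants in each arm have one. An outcome set among stroke patients answers a different question: given a stroke, how bad was it? Membership of that group is decided after randomisation by the very event CEP is intended to reduce. If CEP works, the stroke patients in the two arms are differently selected, and a difference in severity between them mixes the effect on severity with the effect on who has a stroke.

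The practical risk is misreading. A device that prevents mild and severe strokes in equal proportion would show no difference in severity. One that prevents proportionately more mild strokes would appear to cause worse strokes even if it also reduced severe ones.

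For the smRSq there is a further gap. Section 6.1 cites a near 6-fold higher risk of death within 30 days after TAVI-associated stroke, but outcome 10 does not say whether a stroke patient who dies before 6-8 weeks or 12 months is scored or drops out.

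**Working it through.** **Inputs from the protocol.** Section 14.2: "If the proportion experiencing the primary outcome is 3% in the control arm, we will require 7652 patients" for a "33% relative risk reduction (risk ratio 0.67) to 2" per cent; "Assuming 1% losses/withdrawals we will recruit 7730, for 80% power and 5% significance". Section 14.2.1: "the sample size was increased from 7730 to 9712". Allocation is 1:1, so 4856 per arm.

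**Reproducing the plan's figure.** For two proportions, two-sided 5%, 80% power, no continuity correction:

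n per arm = [1.96 × √(2 × 0.025 × 0.975) + 0.8416 × √(0.03 × 0.97 + 0.02 × 0.98)]² / 0.01² = 3826

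The total is 7652, and 7652 / 0.99 rounds up to 7730. Both match. The design stroke risk ratio is therefore 0.02 / 0.03 = 2/3. The protocol gives no calculation for severity or disability.

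**Relation between the two ratios.** Every severe stroke is a stroke, so within an arm:

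P(severe | stroke) = P(severe) / P(stroke)

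Dividing the CEP arm by the control arm:

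RR(severe among strokes) = RR(severe, all participants) / RR(stroke)

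At RR(stroke) = 2/3, the stroke-only ratio is the all-participant ratio times 1.5. The severe share of strokes cancels out. The same relation holds for disabling stroke. If CEP had no effect on stroke (ratio 1), the two ratios would coincide, so the distortion grows with the effect the trial is powered to find.

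**Illustration.** Expected strokes at 9712, ignoring losses: 4856 × 0.03 = 146 control and 4856 × 0.02 = 97 CEP. The severe share of control strokes is not in the protocol. It is assumed to be 25% here; the two ratio columns are the same for any share.

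| Effect of CEP on severe stroke | Severe strokes, control v CEP | RR, all participants | Severe share among strokes, control v CEP | RR among strokes |
|---|---|---|---|---|
| Halved | 36 v 18 | 0.50 | 25% v 18.75% | 0.75 |
| Cut by a third, as for all strokes | 36 v 24 | 0.67 | 25% v 25% | 1.00 |
| Cut by 20% | 36 v 29 | 0.80 | 25% v 30% | 1.20 |
| Unchanged | 36 v 36 | 1.00 | 25% v 37.5% | 1.50 |

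The stroke-only ratio points the wrong way whenever the all-participant ratio for severe stroke lies between 2/3 and 1.

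**Precision of the all-participant estimate.** Power at 4856 per arm, two-sided 5%, to detect a one-third cut in severe stroke:

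- assumed severe share 10% (0.3% v 0.2%): about 17%
- assumed severe share 25% (0.75% v 0.5%): about 35%
- assumed severe share 40% (1.2% v 0.8%): about 51%

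**The case against.** The best defence is that section 7.2 says who is assessed, not how the arms are compared. NIHSS for a stroke and disability after a stroke have no meaning without a stroke. No test or denominator is given, section 14.1 could be read as an intention-to-treat risk ratio, and a binary cut-off at NIHSS 10 fits incidence of severe stroke in everyone. The SAP may say exactly that. This stands in part: a reader might infer that the protocol commits to a stroke-only comparison, and it does not go that far. But the restricted population is written three times, most of the other clinical outcomes in section 7.2 are labelled as incidences while these two are not, and a risk ratio applied to an outcome defined in stroke patients most naturally gives the distorted figure.

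Three other inferences go too far:

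- **That disabling stroke enters no comparison of all participants.** The win ratio includes it. It is blended there with death and non-disabling stroke, so it yields no estimate for disabling stroke alone.
- **That stroke mechanism has the same fault.** Section 7.1.3 says only: "Any difference in stroke mechanism between the arms of the trial will be explored in the secondary analyses". It sets no stroke-only denominator, and embolic and non-embolic stroke by randomised arm is equally consistent with it.
- **That the plan would produce a statistically significant false signal of harm.** If severe stroke is unchanged and 20% of control strokes are severe (an assumption), the stroke-only comparison is 20% v 30%, z = 0.10 / √(0.2 × 0.8 / 145.7 + 0.3 × 0.7 / 97.1) = 1.75, short of 5% significance. The same formula gives about 1.1 at a 10% share and 3.1 at 40%, so significance depends on a figure the protocol does not give. The pattern, with only milder strokes prevented, is also hypothetical.

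It is fair too that these are two of thirteen secondary outcomes and that the primary analysis is unaffected.

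**Conclusion.** The concern holds as a fault in how outcomes 9 and 10 are defined. Their population is formed by the primary outcome, while the purpose of outcome 9 and the secondary objective concern prevention in all participants. If the arms are compared within that population, the severe-stroke risk ratio is multiplied by 1.5 at the design effect. This factor needs only the protocol's 3% and 2%; a smaller true effect on stroke would give a smaller factor. The counts in the table also rest on an assumed severe share. It is not established that the final analysis will be done this way, because the protocol fixes no denominator and the SAP is not shown. The change should be made because it costs little and removes the ambiguity.

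**What to change.** In section 7.2, with matching edits to the synopsis and the section 7 table:

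- **Outcome 9:** incidence of severe stroke within 72 hours or by discharge if sooner, meaning NIHSS 10 or more, with fatal stroke counted as severe.
- **Outcome 10:** incidence of disabling stroke, meaning a stroke in that window followed by disability at a pre-stated smRSq cut-off at each scheduled time. The cut-off should agree with the definition of disabling used for the win ratio, and death after such a stroke should count as an event.
- **Analysis:** both in the section 14.3 intention-to-treat population, with risk ratio and risk difference as in section 14.1, counting participants without stroke as non-events.
- **Supportive description:** keep the NIHSS and smRSq distributions among stroke patients, with a note that they are not randomised comparisons.

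The data are already planned, so no extra collection is needed. The cost is not wording alone, because the disability cut-off is a substantive choice to be fixed before unblinding. The estimates will also be imprecise, as the power figures show, so they should be presented with intervals and not read as firm tests. If the SAP already sets these denominators, the protocol text need only be aligned with it.
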